#### **ECG**

Fridericia's formula (QTcF) will be used to calculate the heart rate-corrected QT interval (msec) based on the heart rate (HR bpm) and QT (msec) for centrally read data. These calculated QTc values will be used in ECG summary tables and listings. The formula is as follows:

QTcF (in msec) =QT/(RR)1/3

Project Document Version No.: 4.0; Document Effective Date: 30 October 2023

CONFIDENTIAL

RECORDATI AG, Rare Diseases Branch LCI699-RECAG-NI-0596

Statistical Analysis Plan

Results for each ECG parameter will be summarized at each visit for observed data and for changes from baseline.

The overall ECG assessment as determined by the investigator will be reported as "Clinical Significant – Yes", or "Clinical Significant – No" and summarized by visit and across visits. A shift table of overall ECG assessment from baseline to the most extreme post-baseline value will be presented.

Additionally, the highest post-baseline value for QTc interval (using Fridericia's correction) will be summarized descriptively as a categorical variable. Each QTcF value for a given subject will be grouped into 3 categories:

- QTcF interval ≥ 450 < 480 msec
- QTcF interval ≥ 480 < 500 msec
- QTcF interval ≥ 500 msec

The largest post-baseline change in QTcF measures will also be analysed as categorical variables. The change in QTcF in as given subject will be grouped into 2 categories:

- QTcF interval increases from baseline ≥ 30 msec
- QTcF interval increases from baseline ≥ 60 msec

Relevant ECG data will also be displayed in separate listings for:

- Subjects who shifted from normal or abnormal not clinically significant at baseline to abnormal clinically significant during the treatment period
- Subjects who had an abnormal clinically significant assessment at any time during the study
- Subjects who ever had a QTcF interval increase from baseline ≥ 30 msec during the treatment period
- Subjects who ever had any value of QTcF interval ≥ 450 msec at any visit

#### CS-Specific Physical examination

The results of physical examination of participants will be summarized descriptively at for baseline, all post-baseline visits with number and percentages of physical examination performed (yes/no), any abnormal findings (yes/no), and body systems as per the eCRF.

A participant level listing will be provided for physical examination with all required details as per the eCRF.

#### 5.9.5 Extent of Exposure

The details of treatment exposure with osilodrostat will be summarized descriptively with number and percentages of dose up- and/or down-titration regimens, and reasons for titration, and duration of treatment.

If patients did not have temporary discontinuation, the duration of exposure will be Duration of exposure (weeks) = (min (date of last date of study treatment, date of early termination, date of death) – date of first dose date of treatment + 1)/7

If patients had temporary discontinuation, the duration of exposure will be assessed specially case by case, the outcome of the case-by-case assessment will be documented in the Analysis Dataset Model (ADaM) related documents.

A summary of duration of exposure to study treatment will include categorical summaries and continuous summaries using appropriate unit of time.

Project Document Version No.: 4.0; Document Effective Date: 30 October 2023

CONFIDENTIAL

TP-GDO-WW-096-09 Effective Date: 22 Dec 21

Related to: SOP-GDO-WW-019 Page 27 of 31

A participant level listing will be provided for treatment exposure with all required details collected as per the eCRF.

Due to the high rate of missing end of treatment dates, the summary of exposure tables will be conducted by using two below approach A and B for the imputation of last date of exposure.

- A. If end of study reason was due to adverse event, death, osilodrostat permanently discontinued, administrative reasons, end of retrospective follow-up period and last recorded dose did not change to 0mg prior to the end of study, the end of study date will be considered as the last date of exposure i.e., the end of treatment date. If last recorded dose changed to 0mg prior to the end of study, then the date when dose changed to 0mg will be considered as the last date of exposure. For other end of study reasons, the end of treatment date will be considered to be missing.
- B. If treatment discontinuation date is not available and last recorded dose did not change to 0mg prior to the end of study, the end of study date will be considered as end of treatment date i.e., the last date of exposure. If last recorded dose changed to 0mg prior to the end of study, then the date when dose changed to 0mg will be considered as the last date of exposure.

#### 5.10 Subgroup Analysis

- i) Selected demographics and patient exposure by subgroups
  - (1) Patient disposition
  - (2) Summary of demographic and baseline disease characteristics
  - (3) Concomitant medications
  - (4) Summary of duration of exposure to Osilodrostat
  - (5) Summary of dose change from initial dose by visits
- ii) Selected efficacy endpoints by subgroups
  - (1) Proportion of mUFC response by (week 4 to 60) mITT and On-treatment population
  - (2) Change in mUFC from baseline by visits in mITT and On-treatment population
  - (3) Proportion of salivary cortisol response by (week 4 to 60) mITT and On-treatment population
  - (4) Proportion of composite measures of cortisol level response by (week 4 to 60) mITT and On-treatment population
  - (5) Change in serum cortisol from baseline by visits in mITT and On-treatment population.
- iii) Selected safety endpoints by subgroups
  - (1) Overview of adverse events
  - (2) Summary of adverse events of special interests by system organ class and preferred term

#### 5.11 Handling of Missing and Uninterpretable Data

#### 5.11.1 Missing data

Based on the nature of the study (observational, non-comparative, retrospective), missing data will not be replaced in the statistical analysis of primary and secondary endpoints.

If there is a significant number of missing values for a subject (or if there is confirmed data appearing spurious), a decision will be made following consultation with the sponsor regarding the handling of these data in summaries, prior to DB lock.

Project Document Version No.: 4.0; Document Effective Date: 30 October 2023

CONFIDENTIAL

Only missing dates will be imputed where applicable and the imputation rule corresponding to missing date is given in section 5.10.2 below.

#### 5.11.2 Missing or incomplete dates

In all listings, missing or incomplete dates should be left as they have been recorded. However, in determining treatment period and/or days since a certain time point, the following conservative approach will be used to impute the missing date values:

#### **Medical History/Disease Diagnosis**

- Missing/incomplete dates will be assumed to have occurred prior to any study treatment, unless there is evidence to prove otherwise
- Partial dates should be reviewed to ensure they did not occur following any study treatment.

#### **AE/Concomitant Medication (Conmed)**

- Day only missing
  - a. If year/month of AE/Conmed equals year/month of the first dose date, then impute start day of the first dose date
  - b. If year of AE/Conmed equals to the year of the first dose date and month of AE/Conmed is less than the month of the first dose date, then impute last day of the month
  - c. If year of AE/Conmed equals to the year of the first dose date and month of AE/Conmed is greater than the month of the first dose date, then impute first day of the month
  - d. If year of AE/Conmed is less than the year of the first dose, then impute last day of the month
  - e. If year of AE/Conmed is greater than the year of the first dose, then impute first day of the month
- Month/Day only missing
  - a. If year of AE/Conmed equals year of the first dose date, then impute start day and month of the first dose date
  - b. If year of AE/Conmed is less than the year of the first dose date, then impute 31Dec
  - c. If year of AE/Conmed is greater than the year of the first dose date, then impute 01Jan
- · Start date is completely missing
  - a. If the first dose date is greater than the AE/Conmed end date, then the AE/Conmed start date equals the AE/Conmed end date
  - b. If the first dose date is less than the AE/Conmed end date, then the AE/Conmed start date equals the start date of first dose
  - c. If the AE/Conmed end date is missing, then the AE/Conmed start date equals the start date for the first dose
- Imputed start date, where end date is not missing
  - a. Check, if the imputed AE/Conmed start date is greater than the AE/Conmed end date, then the imputed start date should be updated to match the AE/Conmed end date

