**CONFIDENTIAL** 

#### Method of Osilodrostat use/ titration

The participants will be classified as follows:

- 1) **Block-and-replace:** Patients who are taking glucocorticoids as concomitant medication less than 2 weeks after initial Osilodrostat.
- 2) *Initial titration followed by block-and-replace:* Patients who initiated Osilodrostat and after at least 2 weeks, started taking glucocorticoids as concomitant medication.
- Titration only: Patients who did not take glucocorticoids as concomitant medications while taking osilodrostat

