#### 5.3.6 Stratified Analysis

Project Document Version No.: 4.0; Document Effective Date: 30 October 2023

CONFIDENTIAL

RECORDATI AG, Rare Diseases Branch LCI699-RECAG-NI-0596

Statistical Analysis Plan

For the potential confounding identification objective, participants will be stratified if they received or did not receive other therapies for Cushing's syndrome (regardless of the type of therapy) from start of study treatment to week 12. The statistical null hypothesis states that the response rates at the end of the 12-week period (i.e., at Week 12) are the same between the participants with/without non-study CS treatment. To test this hypothesis, a Cochran-Mantel-Haenszel (CMH) exact test by non-study CS treatment (yes/no) will be performed using the ITT.

If the 2-sided p-value is  $\leq$  0.05, and the odds ratio (non-study CS medication treatment yes vs. no) is > 1, the null hypothesis will be rejected and the response rate at week 12 in the non-study CS treatment yes group will be considered higher than that in the non-study CS medication treatment no group.

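### Some incompletely dated concomitant drugs are given the first osilodrostat dose date as their start, which can misclass later glucocorticoid starts and later added Cushing's therapies

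*SAP*

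**What the plan says.** SAP 5.11.2 has one set of start-date rules for adverse events and concomitant medication together. Its scope is general: "in determining treatment period and/or days since a certain time point, the following conservative approach will be used". Three situations send a concomitant drug's start to the first osilodrostat dose:

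- **Day and month missing, first-dose year:** "If year of AE/Conmed equals year of the first dose date, then impute start day and month of the first dose date".
- **Day missing, first-dose month:** "If year/month of AE/Conmed equals year/month of the first dose date, then impute start day of the first dose date".
- **Start wholly missing:** either "If the AE/Conmed end date is missing, then the AE/Conmed start date equals the start date for the first dose", or "If the first dose date is less than the AE/Conmed end date, then the AE/Conmed start date equals the start date of first dose".

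Other incomplete dates go elsewhere. For a day-only gap in the first-dose year, the rule is: "month of AE/Conmed is greater than the month of the first dose date, then impute first day of the month". A year-only date in a later year becomes 1 January, and dates in an earlier month or year go to the end of that period, before first dose.

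Two analyses depend on when a concomitant drug started:

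- SAP 3.5 (method of use/titration) defines block-and-replace as "Patients who are taking glucocorticoids as concomitant medication less than 2 weeks after initial Osilodrostat". A glucocorticoid started at 2 weeks or later puts the patient in the group with initial titration followed by block-and-replace.
- SAP 5.3.6 splits the ITT population by whether other Cushing's therapies were received "regardless of the type of therapy) from start of study treatment to week 12", and compares Week 12 response with an exact test.

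Neither section has its own rule for incomplete dates. SAP 5.8 sends partial medication dates to 5.11.2.

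**The concern.** The SAP calls the approach conservative. That fits adverse events, where a doubtful event should count as arising on treatment. It does not carry over to classifying how osilodrostat was used, because the first-dose date is itself an answer to the question being asked. Delay is set to zero, so the record always falls under 2 weeks and always inside the window to Week 12.

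Two things are at stake. How osilodrostat is dosed and titrated is a stated research question (protocol section 7), and SAP 5.10 reports exposure, dose change, response and adverse events by subgroup. Patients who were titrated first and given a glucocorticoid later would bring that dosing pattern into the block-and-replace group. In 5.3.6, a therapy added after the Week 12 sample cannot have affected that sample, yet it would place the patient in the stratum meant to isolate co-treatment.

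**Working it through.** The plan gives no figure on this point to reproduce. The check follows the rule through and then illustrates how often it could misplace a record.

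**1. Direction.** In the three branches the imputed delay is 0 days. If the true delay D is 0 or more, the error is −D, so it is never towards a later start. The closing check in 5.11.2 pulls an imputed start back to the end date, so it also acts only towards earlier dates.

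**2. Examples.**

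| First dose | True start | Known | True day | Imputed day | Effect |
|---|---|---|---|---|---|
| 15 Jan 2021 | 20 Nov 2021 | year | 309 | 0 | crosses both cuts |
| 2 Mar 2021 | 30 Mar 2021 | month, year | 28 | 0 | crosses the 2-week cut |
| 15 Jan 2021 | 20 Nov 2021 | month, year | 309 | 290 | no change of class |

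The second branch cannot take a post-Week-12 start to day 0, because both dates lie in one month. The first-of-month and 1 January rules do not use the first-dose date but can still cross a cut. With first dose on 15 January and true start on 25 April, day 100 becomes day 76. With first dose on 20 December and true start on 1 September, day 255 becomes day 12.

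**3. Share of year-only, first-dose-year records that truly start late.** Assumption, not from the documents: first dose is equally likely on each day of a 365-day year, and drug start is equally likely on each day from first dose to 31 December. With m days left, P(D ≥ c) = (m − c)/m. Averaging over first-dose days:

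- D ≥ 14 (c = 14): (1/365) × Σ(1 − 14/m), m = 15 to 365, = 305.8/365 = 0.838.
- D > 84 (c = 85): (1/365) × Σ(1 − 85/m), m = 86 to 365, = 156.5/365 = 0.429.

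Weighting every pair of first dose and start equally instead gives (365 − c)(366 − c)/(365 × 366):

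- c = 14: 351 × 352/133,590 = 0.925.
- c = 85: 280 × 281/133,590 = 0.589.

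The ranges are therefore 84% to 93% and 43% to 59%. For the first-dose-month branch in a 30-day month, (1/30) × Σ(1 − 14/m), m = 15 to 30, = 5.592/30 = 0.186.

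**4. Share of truly late starts that end in the wrong class.** This is a different denominator. All 5.11.2 start-date branches were applied to every first-dose day of 2021, with true starts spread evenly over 182, 364 or 1,095 days after first dose and no end date used.

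| What is missing | True D ≥ 14 classed under 14 | True D > 84 classed by Week 12 |
|---|---|---|
| Day only | 8.7% / 4.2% / 1.4% | 15.0% / 5.3% / 1.5% |
| Day and month | 76.7% / 51.8% / 16.8% | 86.4% / 61.5% / 18.0% |
| Whole date (end date missing or after first dose) | 100% | 100% |

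The day-only and year-only rows include later months and years, so they also count cut crossings from the first-of-month and 1 January rules. Their size depends heavily on how long after first dose drugs were added.

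**The case against.** Several limits on the point stand.

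- A reader might infer that every partial date moves to first dose, or that the rule always pushes one way. Neither is so. Other branches use the first of the month, 1 January or a pre-dose date, and a drug begun before first dose can be moved later. The one-way error holds only for true post-dose starts.
- A reader might take 84% as the error rate. It excludes drugs begun with or before osilodrostat, which the rule classes correctly if they were still being taken and which are the typical block-and-replace case. It also counts records, whereas a patient changes class only if no other adequately dated record already fixes the class.
- Titration-only patients took no glucocorticoid while on osilodrostat, so re-dating a real post-dose glucocorticoid moves nobody out of that group.
- SAP 5.3.6 is not the only view of response by other therapy. The treatment-naïve, switch and combination subgroups in 3.5 feed the response tables in 5.10, and the combination group has no time window.
- For 5.3.6, sending doubtful cases to the co-treated stratum keeps the other stratum clean. That is a defensible choice, but it should be made openly and its effect shown. The documents do not settle the direction of any bias in the odds ratio.
- Data queries (protocol 8.6), scheduled collection of concomitant drugs and the pre-lock review of missing data (SAP 5.11.1) should reduce the number of incomplete dates. They do not change what happens to those that remain.

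The SAP also does not name 3.5 or 5.3.6 as users of the imputed dates. The link rests on the general wording of 5.11.2 and on the absence of any other rule.

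**Conclusion.** The point holds for the three branches that default to first dose. Applied as written, they class a true later glucocorticoid start as block-and-replace instead of initial titration followed by block-and-replace, and they can count a Cushing's therapy added after Week 12 as received by Week 12. SAP 5.3.5 plans no check on date handling.

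The size among about 100 patients cannot be calculated, because the documents give no count of incompletely dated concomitant drugs. The 84% and 43% are illustrations that rest on the uniform post-dose start.

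A reader might infer that the primary result is at risk. It is not: the overall ITT proportion with mUFC at or below the ULN at Week 12 uses no concomitant-drug dates. What is exposed is one descriptive subgroup definition and one stratified comparison.

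**What to change.** In SAP 5.11.2, keep the first-dose default for adverse events and for the prior/concomitant flag, and state that it is not used for the 3.5 titration subgroup or the 5.3.6 stratum. For those two:

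1. If an adequately dated record already settles the patient's class, use it.
2. Otherwise derive the earliest and latest possible start from the partial date, the end date and, if the eCRF holds it, the visit where the drug was first recorded. Assign a class only when both dates fall in it.
3. Report the remaining patients in a timing-unknown row.
4. Repeat the 5.3.6 table with the timing-unknown patients placed in each stratum in turn.

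The cost is a paragraph of SAP wording, one derived variable for earliest and latest start, and two reruns of one table. The downside is an extra category and slightly smaller named subgroups. Section 5.11.2 already has separate rules for medical history and for osilodrostat dosing dates, so a purpose-specific rule fits its structure.

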#### Osilodrostat Administration date

- · Day only missing of first dose date
  - a. Imputed missing day as 15 of the month.

Project Document Version No.: 4.0; Document Effective Date: 30 October 2023

CONFIDENTIAL

- · Day only missing
  - a. Imputed missing day as 15 of the month, unless other dates related to the dose change are occurring before the 15, in that case the day should be the same of the event occurring in concomitance.
- Day and month missing
  - a. If the dose change is related to an event (adverse event, study discontinuation, etc.) imputed missing month as the month of the event or the visit month, and impute missing day as 15 unless the other dates related to the dose change are occurring before the 15, in that case the day should be the same of the event occurring in concomitance.

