10.1 Definitions

Adverse events (AEs)

An AE is any untoward medical occurrence in a patient or clinical study participant administered a pharmaceutical product, whether or not considered related to the product. An AE can therefore be any unfavourable and unintended sign (including an abnormal laboratory finding, for example), symptom, or disease (new or exacerbated) temporally associated with the use of a product.

Treatment-emergent adverse events (TEAEs)

Any AE with an onset date on or after the study drug start date and no later than 30 days after last dose of study drug, or any worsening of any AE on or after the study drug start date.

Serious adverse events (SAEs)

An SAE is any AE that:

- Results in death.
- Is life-threatening. (Note: The term 'life-threatening' in the definition of 'serious' refers to an event in which the subject was at risk of death at the time of the event; it does not refer to an event that hypothetically might have caused death if it were more severe).
- Requires inpatient hospitalization or prolongation of existing hospitalization.
- Results in persistent or significant disability/incapacity.
- Is a congenital anomaly/birth defect.

• Is an important medical event. Important medical events that may not result in death, be life-threatening, or require hospitalization may be considered an SAE when, based upon appropriate medical judgment, they may jeopardize the patient and may require medical or surgical intervention to prevent one of the outcomes listed in this definition.

Adverse drug reaction (ADR)

An ADR is defined as a response to a medicinal product which is noxious and unintended. Response in this context means that a causal relationship between a medicinal product and an AE is at least a reasonable possibility, i.e., the relationship cannot be ruled out.

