- d. Osilodrostat initiation dose and up- and/or down-titration regimens (including dates) and reasons for titration will be recorded in the database during the study.
- e. All prior medications taken within 6 months prior to the first dose of Osilodrostat must be collected.
- f. Baseline mean urinary free cortisol data can be collected within 1 month prior to osilodrostat initiation.
- g. Footnote-a is not applicable to the following assessments: prior medications, concomitant medications and mean urinary free cortisol.
- \*End of data collection may be due to earlier of loss-to-follow-up, death, end of retrospective follow-up period or treatment discontinuation.
- \*CBC includes WBC, RBC, Haemoglobin, Haematocrit, MCV, MCH, MCHC, RDW, Platelet Count, MPV and Differential (Absolute and Percent Neutrophils, Lymphocytes, Monocytes, Eosinophils, and Basophils).
- &CMP includes Albumin, Alkaline Phosphatase, ALT, AST, Calcium, Carbon Dioxide, Chloride, Creatinine with GFR Estimated, Glucose, Potassium, Sodium, Total Bilirubin, Total Protein, (Blood) Urea Nitrogen.
- @ For list of CS-specific examination findings, please refer to protocol section 8.3.2.

As this is a descriptive study, the effectiveness and safety endpoints will be summarized descriptively. No formal statistical hypothesis testing will be performed.

Data from an approximately 100 patients meeting the inclusion/exclusion criteria in France will be collected.

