
Baseline is defined as the available value at the time of osilodrostat initiation or the closest value within 2 weeks prior to osilodrostat initiation.

Change from baseline will be calculated as the post-baseline value of interest minus the baseline value. Percent change from baseline is defined as:  $100 \times [(post-baseline - baseline) / baseline]$ . If all baseline values are missing for a particular variable, the change from baseline and percent change from baseline will not be calculated.

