#### 5.3.3.11 Proportion of participants who experienced TEAE and AESI

A treatment-emergent adverse event (TEAE) is defined as an AE that begins or that worsens in severity after at least one dose of osilodrostat has been administered. The start date of adverse events will be compared with date of first dose of osilodrostat and the date of the earlier of loss to follow-up, death, the end of the retrospective follow-up period or treatment discontinuation occurs, whichever is earlier.

TEAE will be coded according to the latest Medical Dictionary for Regulatory Activities (MedDRA) terms and summarized by MedDRA System Organ Class (SOC) and Preferred Term.

Adverse Events of Special Interest (AESI) will be defined as following AEs:

- Adrenal hormone precursor accumulation-related AEs
- Hypocortisolism-related AEs
- Pituitary tumour enlargement-related AEs
- Arrhythmogenic potential and QT prolongation AEs

All AEs will be assessed according to incidence, grade, causality, outcome, action taken and seriousness. The details are provided in the safety analysis section 5.10.1 below.

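### When the first-dose day is missing, setting it to the 15th can remove fully dated on-drug adverse events from the TEAE summaries

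*SAP*

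**What the plan says.** SAP 5.11.2 introduces its date rules by stating that "the following conservative approach will be used to impute the missing date values". Under the Osilodrostat Administration date subheading, a first-dose date with only the day missing is handled by "Imputed missing day as 15 of the month", with nothing further. The next rule, for other administration dates, uses the same day but adds an escape: "unless other dates related to the dose change are occurring before the 15". The first-dose rule has no such clause.

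The first-dose date then decides TEAE status. SAP 5.3.3.11 defines a TEAE as "an AE that begins or that worsens in severity after at least one dose of osilodrostat has been administered" and gives the comparison: "The start date of adverse events will be compared with date of first dose of osilodrostat". Protocol 10.1 agrees: "Any AE with an onset date on or after the study drug start date".

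The AE part of SAP 5.11.2 changes only missing or partial AE dates. An AE in the first-dose month with its day missing is moved to the first-dose date. It is then pulled back to its end date if that end date is earlier. A complete AE date is left alone and is compared directly with the imputed 15th.

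Baseline is also set by timing. SAP 5.2 says: "Baseline is defined as the available value at the time of osilodrostat initiation or the closest value within 2 weeks prior to osilodrostat initiation". For mUFC, footnote f to SAP Table 1 is wider: "Baseline mean urinary free cortisol data can be collected within 1 month prior to osilodrostat initiation".

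**The concern.** For a safety analysis, a conservative rule for an uncertain first dose is one that does not discard events that may have occurred on drug. The 15th can discard them. If the true start was earlier in the month, every fully dated event between the true start and the 14th is treated as pre-dose.

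The result is also inconsistent within the section. A same-month AE with no recorded day is generally kept as treatment-emergent, unless its end date falls before the imputed first dose. A same-month AE with an exact date before the 15th is dropped. The better-documented event is the one lost.

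At stake are early on-drug events in the TEAE tables of a study meant to support a supplemental application. A second, less certain risk is that a value taken on drug before the 15th is accepted as baseline for change-from-baseline summaries.

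**Working it through.** The plan gives no figure for this rule, so there is nothing to reproduce. The check counts days.

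**Inputs.** Imputed day 15 (SAP 5.11.2). TEAE if onset is on or after first dose (Protocol 10.1, SAP 5.3.3.11). Baseline look-back of 14 days (SAP 5.2). About 100 patients (SAP 5.12). *Assumptions, not in the documents:* true start day d uniform over the month, constant daily AE rate, complete AE dates.

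**1. Example.** True first dose on the 3rd, AE on the 9th, laboratory value on the 10th.
- With the true date, the AE is a TEAE and the value is 7 days after first dose.
- With the 15th, the AE falls 6 days before first dose and is pre-treatment. The value falls 5 days before first dose and meets the baseline window.

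**2. Share of imputed patients exposed.** The event loss needs d from 1 to 14: 14/28 = 50.0%, 14/30 = 46.7%, 14/31 = 45.2%. For each such d, 15 − d on-drug days (1 to 14, mean 7.5) are placed before treatment.

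**3. Share of on-drug AEs lost, 30-day month.** On-drug days placed before the 15th, summed over start days: 14 + 13 + … + 1 = 105.
- Denominator A, on-drug days in the calendar month of initiation: 30 + 29 + … + 1 = 465. Loss = 105/465 = 22.6%.
- Denominator B, the first 30 days on drug: 30 × 30 = 900. Loss = 105/900 = 11.7%.
- Among patients who truly started before the 15th: A gives 105/329 = 31.9% (30 + 29 + … + 17 = 329); B gives 105/420 = 25.0% (14 × 30 = 420).

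All of these are conditional on the first-dose day being missing.

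**4. Patients affected.** The rate of missing first-dose days is not given. For assumed rates m, the expected number with a true start before the 15th is 100 × m × 14/30:

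| m | patients |
|---|---|
| 2% | 0.9 |
| 5% | 2.3 |
| 10% | 4.7 |
| 20% | 9.3 |

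**5. Error in the other direction.** For d after the 15th, d − 15 pre-dose days count as on treatment: 1 + 2 + … + 15 = 120 over the 30 start days, or 120/30 = 4.0 days per imputed patient. Imputing the 1st would lose no on-drug days, but would count 1 + 2 + … + 29 = 435 pre-dose days, or 435/30 = 14.5 per imputed patient.

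**6. Baseline.** A value dated day 1 to 14 lies at most 14 days before the 15th, so every post-dose value before the 15th meets the look-back. Imputing the 1st would do different damage. For d of 16 or later (15/30 = 50%), the true look-back begins on day d − 14, which is day 2 or later. All true baseline values would then fall after the imputed start.

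**The case against.** The strongest reply is that nothing shows the problem occurs. The initiation dose and its date are collected (footnote d to the data collection table in both documents), and Protocol 8.6 provides edit checks and queries for missing critical data. SAP 5.9.5 reports many missing end-of-treatment dates but says nothing similar about first doses. Mid-month imputation also errs in both directions by similar amounts (105 against 120 days in step 5). This stands as a limit on size. It does not make the rule conservative: balanced errors still remove known on-drug events.

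A reader might infer more than the documents support:

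- **AESIs are lost.** Not established. SAP 5.3.3.11 defines AESIs by type, and SAP 5.9.1 lists AESI and SAE tables without a treatment-emergent condition. Only Protocol 8.7.9 applies that condition to AESIs. Events dropped as TEAEs also remain in the all-AE listing of SAP 5.9.1, and later worsening can bring one back.
- **A quarter of first-month events disappear.** The 23% refers to the calendar month of initiation. Over the first 30 days on drug it is about 12%.
- **Visit windows shift by their full width.** The Week 4, 8 and 18 windows are ±2 weeks, so two weeks is the half-width. Sites record the assessment closest to each visit, and neither document says visits are re-derived from the imputed date.
- **Baselines are contaminated.** This is possible because SAP 5.2 defines baseline by timing. It needs a value recorded in the gap, and a site-labelled baseline visit could prevent it. The primary endpoint uses no baseline value.
- **The dose-change exception should be extended to first doses.** That clause aligns a dose change with a date related to it. An AE is not normally the reason for a first dose, and moving the first dose to the AE date would turn genuinely pre-dose events into TEAEs.

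**Conclusion.** The point holds in a narrow form. When only the first-dose day is missing, SAP 5.11.2 can class a fully dated on-drug AE as pre-treatment and remove it from the TEAE summaries, and no other section corrects this. The AESI summary is affected only if it follows the treatment-emergent restriction of Protocol 8.7.9. Calling the approach conservative is wrong for safety, and the outcome is inconsistent with the same section's usual handling of same-month AEs with a missing day.

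For patients with an imputed first-dose day, the expected loss is about 23% of on-drug AEs dated in the calendar month of initiation, or about 12% of AEs in the first 30 days on drug. Both rest on a uniform start day, a 30-day month and a constant AE rate. A higher AE rate soon after initiation would change them. The effect on the whole study cannot be sized, because the number of missing first-dose days is unknown. At assumed rates of 2% to 20%, about 1 to 9 of 100 patients would have a true start before the 15th. Misassigned baselines are a possibility to guard against, not a demonstrated error. This is a minor point that is cheap to correct.

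**What to change.** Amend SAP 5.11.2 as follows.

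- **TEAE flag only.** When the first-dose day is imputed, count any AE dated in the first-dose month as treatment-emergent unless the record shows that it began before osilodrostat. Equivalently, for this flag use the earliest first-dose date consistent with the record.
- **Exposure duration.** Keep the 15th.
- **Baseline.** For these patients use the value that the site recorded at the baseline visit. Do not move the baseline date to the 1st, and do not set the first dose to the AE date.
- **AESIs.** State whether the AESI summary is restricted to treatment-emergent events, so that SAP 5.9.1 and Protocol 8.7.9 agree.
- **Reporting.** Give the number of patients with an imputed first-dose day.

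The cost is a few lines of text and one derived flag. The downside is that some truly pre-dose events in that month will count as TEAEs. If the record offers nothing to narrow the start date, an average of 14.5 pre-dose days per imputed patient would be open to this, against 4.0 under the present rule. Any record showing the patient not yet on osilodrostat reduces that.
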